#### **9.1.4 Microbiological Outcomes per Baseline Pathogen for Follow-up**

Microbiological outcomes by baseline pathogen will be determined by the sponsor according to the following criteria established for each infection site at FU.

##### **9.1.4.1 HABP/VABP/HCABP**

- **Sustained Eradication:** Absence of the baseline Gram-negative pathogen from an appropriate clinical specimen after TOC. If it is not possible to obtain an appropriate clinical culture and the subject has a successful clinical response after TOC, the response will be presumed sustained eradication.
- **Recurrence:** Recurrence of the baseline Gram-negative pathogen from an appropriate clinical specimen taken after TOC, and the TOC culture is negative.
- **Indeterminate:** No culture obtained from an appropriate clinical specimen or subject received additional antibacterial therapy for the treatment of the current infection. Indeterminate at TOC will be carried forward.
- **Persistence:** Persistence at TOC will be carried forward.

##### **9.1.4.2 cUTI**

- **Sustained Eradication:** A culture taken any time after documented eradication at TOC, and a urine culture obtained at FU shows that the baseline uropathogen found at entry at  $\geq 10^5$  CFUs/mL remains  $< 10^3$  CFUs/mL.
- **Recurrence:** A culture taken any time after documented eradication at TOC, up to and including FU that grows the baseline uropathogen  $\geq 10^3$  CFUs/mL.
- **Indeterminate:** No urine culture or subject received additional antibacterial therapy for the treatment of the current infection. Indeterminate at TOC will be carried forward.
- **Persistence:** Persistence at TOC will be carried forward.

##### **9.1.4.3 BSI/Sepsis**

- **Sustained Eradication:** Absence of the baseline Gram-negative pathogen from a blood culture or other primary source after TOC as applicable. In the case of sepsis, if the subject has a successful clinical outcome after TOC and it is not possible to obtain an appropriate clinical culture, the response will be presumed to be sustained eradication. In the case of BSI, if the subject has a successful clinical outcome and the investigator considers no further need to obtain a clinical culture, the response will be presumed to be eradication.

- **Recurrence:** Recurrence of the baseline Gram-negative pathogen from a blood culture or other primary source after TOC and the TOC culture is negative.
- **Indeterminate:** No culture from an appropriate clinical specimen or subject received additional antibacterial therapy for the treatment of the current infection. Indeterminate at TOC will be carried forward. . The exception to this is noted in 9.1.4.3 definition of Eradication.
- **Persistence:** Persistence at TOC will be carried forward.

### 9.1.5 New Pathogens

New pathogens that emerge on or after Day 3 will be categorized as either superinfection or new infection as follows: Superinfection and new infection will be listed by Gram-negative pathogen and the others.

- **Superinfection:** The identification from an appropriate clinical specimen of a new pathogen from the original infection site.
- **New Infection:** The identification from an appropriate clinical specimen of a new pathogen from an infection site different from the original infection site.

### 9.1.6 Per Subject Microbiological Outcomes

As shown in Table 9-1, subjects who experience eradication of all baseline Gram-negative pathogens at EOT and TOC will be considered “Eradication” and subjects who experience persistence of any baseline Gram-negative pathogen will be considered “persistence.” Subjects whose experiences are other than above will be considered “indeterminate.” At FU, subjects who experience sustained eradication of all baseline Gram-negative pathogens after documented eradication at the TOC will be considered “sustained eradication” and subjects who experience eradication at TOC but recurrence of any baseline Gram-negative pathogen will be considered as “recurrence”, and subjects who are considered as “persistence” at TOC will be “persistence.” Subjects whose experiences are other than above will be considered “indeterminate.”

**Table 9-1 Per Subject Microbiological Outcome**

Visit	Per Subject Microbiological Outcome	Definition
EOT, TOC	Eradication	Eradication of all baseline Gram-negative pathogens
	Persistence	Persistence of any baseline Gram-negative pathogens
	Indeterminate	Other than those above
FU	Sustained eradication	Sustained eradication of all baseline Gram-negative pathogens after documented eradication at the TOC
	Persistence	Persistence of any baseline Gram- at the TOC
	Recurrence	Recurrence of any baseline Gram-negative pathogens for subjects eradication at the TOC
	Indeterminate	Other than those above

EOT = End of Treatment; FU = Follow-up; TOC = Test of Cure

For the subjects who have Gram-positive pathogens at baseline, the Gram-positive pathogens will be shown in the listing of local microbiological test and not be taken into account in either per pathogen microbiological outcome or per subject microbiological outcome.

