#### **6.4.2 Missing Microbiological or Clinical Outcome**

For clinical and microbiological outcomes, subjects who are lost to follow-up or have missing or "indeterminate" outcomes will be included in the denominator as indeterminate for cure/eradication rate, i.e., considered as not responders. If judged by the investigator that a subject died due to pneumonia, BSI/sepsis or cUTI, the clinical outcome will be considered as clinical failure after the event of death. If a subject died due to other reasons, the clinical outcome will be considered as "indeterminate" after death.

For clinical outcome, if a subject received additional antibiotics for target disease (i.e., baseline infection) before the target date, the outcome will be considered as "clinical failure". If a subject did not receive additional antibiotics for target disease before the target date, the outcome will be considered as "indeterminate".

Missing values for other individual data points will remain as missing unless otherwise specified. All analysis will be based on observed case unless otherwise stated.

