#### **9.1.3.1 HABP/VABP/HCABP**

- **Eradication:** Absence of the baseline Gram-negative pathogen from an appropriate clinical specimen. If it is not possible to obtain an appropriate clinical culture and the subject has a successful clinical outcome, the response will be presumed to be eradication.
- **Persistence:** Continued presence of the baseline Gram-negative pathogen from an appropriate clinical specimen.
- **Indeterminate:** No culture obtained from an appropriate clinical specimen or additional antibacterial therapy for the treatment of the current infection.

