#### **9.1.3.3 BSI/Sepsis**

- **Eradication:** Absence of the baseline Gram-negative pathogen from a blood culture and/or other primary source as applicable. In the case of sepsis, if the subject has a successful clinical outcome and it is not possible to obtain an appropriate clinical culture, the response will be presumed to be eradication. In the case of BSI, if the subject has a successful clinical outcome and the investigator considers no further need to obtain a clinical culture, the response will be presumed to be eradication.

- **Persistence:** Continued presence of the baseline Gram-negative pathogen from a blood culture or other primary source.
- **Indeterminate:** No culture obtained from an appropriate clinical specimen or additional antibacterial therapy for the treatment of the current infection. The exception to this is noted in 9.1.3.3 definition of Eradication.

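### Recurrence at follow-up needs a negative TOC culture that presumed eradications lack, and sustained eradication per subject turns on an undefined word

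*SAP*

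**What the plan says.** **At TOC.** For pneumonia, SAP 9.1.3.1 places presumed eradication inside the category Eradication: when no appropriate culture can be obtained and "the subject has a successful clinical outcome, the response will be presumed to be eradication". SAP 9.1.3.3 has the same rule for sepsis. For BSI it adds that, after clinical success, if the "investigator considers no further need to obtain a clinical culture, the response will be presumed to be eradication".

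**At FU, per pathogen.** Sustained eradication in SAP 9.1.4.1 and 9.1.4.3 names no TOC culture and may itself be presumed. Recurrence is stricter. In pneumonia it is "Recurrence of the baseline Gram-negative pathogen from an appropriate clinical specimen taken after TOC, and the TOC culture is negative". In BSI/sepsis it is growth "from a blood culture or other primary source after TOC and the TOC culture is negative". The same condition stands in SAP 9.2.5.1 and 9.2.5.3 and in Protocol 7.11.4.1 and 7.11.4.3.

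**At FU, per subject.** Table 9-1 defines sustained eradication as "Sustained eradication of all baseline Gram-negative pathogens after documented eradication at the TOC", and SAP 9.1.6 and 9.2.6 use the same phrase. Recurrence in Table 9-1 is "Recurrence of any baseline Gram-negative pathogens for subjects eradication at the TOC", with no documented and no mention of a culture. Everything not listed is indeterminate.

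**Scoring.** Under SAP 6.4.2, indeterminate outcomes are "included in the denominator as indeterminate for cure/eradication rate, i.e., considered as not responders".

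**The concern.** The TOC rules accept eradication without a culture, but one FU definition then asks for the result of that culture, and another asks for documented eradication without saying what that means. Two kinds of subject are affected: one whose baseline pathogen grows again at FU, and one who stays well with no sign of the pathogen.

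The situation is partly built into the schedule. Protocol 8.3 has blood cultured only until a negative result, so a BSI patient who cleared earlier need not have a TOC blood culture. Protocol 8.4 asks for FU cultures only if indicated. A patient who returns with a suspected relapse is thus likely to have an FU culture but may have no TOC culture.

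At stake are secondary endpoints: microbiological outcome at FU, the FU composite, and the bacteremia outcome, which SAP 9.4.1.2 bases on 9.2.4.3 and 9.2.5.3 and which inherits the recurrence condition. If the rules stay as they are, two programmers could produce different FU rates from identical data.

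**Working it through.** The documents state no figure that depends on these definitions, so there is none to reproduce. The check is to place each combination of TOC and FU findings under the rules.

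**Step 1: classify.** Pneumonia or BSI/sepsis, no additional antibacterial therapy. Strict means that documented is culture-proven; lenient means that it includes presumed.

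| TOC eradication | FU finding | Per subject, strict | Per subject, lenient |
|---|---|---|---|
| Negative culture | Negative culture, or no culture with clinical success | Sustained eradication | Sustained eradication |
| Negative culture | Baseline pathogen grows | Recurrence | Recurrence |
| Presumed | Negative culture, or no culture with clinical success | Indeterminate | Sustained eradication |
| Presumed | Baseline pathogen grows | Indeterminate | Indeterminate |

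The last row is the same under both readings. Per pathogen, such a subject fits no FU category:
- Sustained eradication fails because the pathogen is present.
- Recurrence fails because there is no negative TOC culture.
- Persistence at FU is only carried forward from TOC.
- Indeterminate needs a missing culture, additional therapy or an indeterminate TOC outcome.

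Per subject, recurrence keeps the only definition the SAP gives it, so the subject lands in the residual category.

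**Step 2: effect of the last row.** Indeterminate and recurrence are both non-response, so the FU eradication rate is unchanged. For the composite, presumed eradication implies clinical success at TOC, so three clinical outcomes remain at FU. Table 9-3 gives:

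| Clinical outcome at FU | With recurrence | With indeterminate |
|---|---|---|
| Sustained clinical cure | Failure | Indeterminate |
| Indeterminate | Failure | Indeterminate |
| Clinical relapse | Failure | Failure |

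**Step 3: effect of the third row of Step 1.** Under the strict reading the subject moves from responder to non-responder. With sustained clinical cure, the composite moves from Response to Indeterminate.

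**Step 4: size under the strict reading, with assumed rates.** Planned pneumonia group (SAP 4.2 and 4.3): 150 × 0.50 = 75 subjects; 75 × 2/3 = 50 on cefiderocol and 75 × 1/3 = 25 on BAT. Assume a true sustained eradication rate of 40% and vary the share of those responders who were only presumed at TOC. Counted responders = true responders × (1 − share), rounded to whole subjects. Intervals are 95% Clopper-Pearson, the SAP's method.

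| Presumed share | Cefiderocol, n = 50 | BAT, n = 25 |
|---|---|---|
| 0 | 20/50 = 40% (26.4 to 54.8) | 10/25 = 40% (21.1 to 61.3) |
| 25% | 15/50 = 30% (17.9 to 44.6) | 8/25 = 32% (14.9 to 53.5) |
| 50% | 10/50 = 20% (10.0 to 33.7) | 5/25 = 20% (6.8 to 40.7) |

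Under the lenient reading the rate is 40% in every row. The documents give neither the 40% nor the shares.

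**The case against.** A reader might infer that every subject with presumed eradication at TOC is shut out of both FU categories and becomes a non-responder. The documents do not settle that. Documented is undefined, and presumed eradication already counts as Eradication at TOC. SAP 9.1.4.1 and 9.1.4.3 accept presumed sustained eradication without a TOC culture. SAP 9.4.1.2 defines the reported rate as the proportion with all baseline pathogens eradicated at each time point, and Protocol 9.9.2.2 builds the per-patient outcome from the per-pathogen outcomes; neither asks for documentation at TOC. All this stands, so that half of the point is a conflict between rules. The strict reading is still the literal one: SAP 9.1.6 uses documented for sustained eradication, while for recurrence it says only "subjects who experience eradication at TOC but recurrence of any baseline Gram-negative pathogen will be considered as" recurrence.

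A reader might also infer an artificial difference between arms. Take 48% eradication at TOC, 85% of it sustained, and presumed shares of 25% and 50% in the two arms. The strict reading then gives 0.48 × 0.75 × 0.85 = 30.6% and 0.48 × 0.50 × 0.85 = 20.4%, which is 10.2 points apart with identical true outcomes. Every input is assumed and the lenient reading gives no difference, so this does not measure a defect.

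A third argument is that, without a TOC culture, regrowth at FU cannot be told from an infection that never cleared. That is fair as microbiology. But the SAP has already scored the subject as eradicated at TOC, and Table 9-3 gives Failure for both persistence and recurrence. Indeterminate is the one label that does not reflect a positive culture.

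Finally, a relapse treated with further antibacterials before FU meets a separate ground for indeterminate, and clinical relapse gives composite Failure either way. This limits the number of subjects affected but does not close the gap.

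**Conclusion.** The recurrence gap is real and does not depend on how documented is read. A culture-proven return after presumed eradication is not counted as recurrence per pathogen. Per subject it falls to indeterminate, given that recurrence carries its per-pathogen definition. The effect is an undercount of recurrences and a composite of Indeterminate instead of Failure in two of the three possible clinical outcomes. The FU eradication rate does not change. The number of subjects cannot be derived from the documents.

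The sustained-eradication half is conditional. If documented means culture-proven, the FU rate falls in proportion to the share of presumed eradications among responders; if it includes presumed, the loss is zero.

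The point is limited to descriptive secondary endpoints at FU in pneumonia and BSI/sepsis. It would be wrong to conclude that all FU categories assume a TOC culture: among the sustained eradication and recurrence definitions for these sites, only recurrence per pathogen names one. cUTI is unaffected because eradication there always needs a urine culture, and the primary endpoint is unaffected because it is assessed at TOC.

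**What to change.** For pneumonia and BSI/sepsis only:

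- In the recurrence definitions of SAP 9.1.4.1, 9.1.4.3, 9.2.5.1 and 9.2.5.3, replace the negative TOC culture condition with: *and the outcome at TOC was eradication (documented or presumed)*.
- In SAP 9.1.6, Table 9-1 and 9.2.6, reword the condition for sustained eradication as: *after eradication (documented or presumed) at the TOC*.
- List the departure from Protocol 7.11.4.1 and 7.11.4.3 in SAP section 15.

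Leave the cUTI definitions as they are. The cost is SAP wording and derivation programming; no new data are needed.

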### 9.1.7 Definition for Composite of Clinical and Microbiological Outcome

The definition for composite of clinical and microbiological outcome based on possible combinations per subject microbiological outcome and clinical outcome is shown in Table 9-2 for EOT and TOC, and in Table 9-3 for FU.

**Table 9-2 Clinical and Microbiological Outcome: EOT and TOC**

Per Subject Microbiological Outcome	Clinical Outcome	Composite of Clinical and Microbiological Outcome
Eradication	Clinical cure	Response
Eradication	Clinical failure	Failure
Eradication	Indeterminate	Indeterminate
Persistence	Clinical cure	Failure
Persistence	Clinical failure	Failure
Persistence	Indeterminate	Failure
Indeterminate	Clinical cure	Indeterminate
Indeterminate	Clinical failure	Failure
Indeterminate	Indeterminate	Indeterminate

**Table 9-3 Composite Outcome: Follow-up**

Per Subject Microbiological Outcome	Clinical Outcome	Composite of Clinical and Microbiological Outcome
Sustained eradication	Sustained clinical cure	Response
Sustained eradication	Clinical failure	Failure
Sustained eradication	Clinical relapse	Failure
Sustained eradication	Indeterminate	Indeterminate
Persistence	Sustained clinical cure	Failure
Persistence	Clinical failure	Failure
Persistence	Clinical relapse	Failure
Persistence	Indeterminate	Failure
Recurrence	Sustained clinical cure	Failure
Recurrence	Clinical failure	Failure
Recurrence	Clinical relapse	Failure
Recurrence	Indeterminate	Failure
Indeterminate	Sustained clinical cure	Indeterminate
Indeterminate	Clinical failure	Failure
Indeterminate	Clinical relapse	Failure
Indeterminate	Indeterminate	Indeterminate

### 9.1.8 Clinical Pulmonary Infection Score

Clinical pulmonary infection score is a surrogate for diagnosis and treatment response. Points (0, 1, or 2) will be assigned for observed findings for 5 variables, including body temperature, white blood cell (WBC) count, tracheal secretions, partial pressure of arterial oxygen (PaO2), fraction of inspired oxygen (FiO2), and chest radiograph.

### 9.1.9 Sequential Organ Failure Assessment Score

The SOFA score is a scoring system to determine the extent of a subject's organ function or rate of failure. The score is based on 6 different scores, 1 each for the respiratory, cardiovascular, hepatic, coagulation, renal, and neurological systems.

## 9.2 Supplementary Efficacy Assessment

### 9.2.1 Analysis Time Window

Only for supplementary analysis described in Section 9.2, the time window below will be applied (Table 9-4). If there are multiple available values in an analysis time window, the data captured as corresponding visit will be used for analysis. If there is no such data, the closest value to the target day will be used for analysis, and if there are multiple values within the same day, the latest value will be used.

**Table 9-4 Analysis Window**

Time Point	Target Day/Time	Analysis Time Window
End of Treatment	Date of end of last infusion	-1 to + 3 days
Test of Cure	Date of end of last infusion + 7	-3 to + 3 days
Follow-up	Date of end of last infusion + 14	-3 to + 3 days

### 9.2.2 Supplementary Clinical Outcomes for EOT and TOC

#### 9.2.2.1 HABP/VABP/HCABP

- **Clinical Cure:** Resolution or substantial improvement of baseline signs and symptoms of pneumonia including a reduction in SOFA and CPIS scores, and improvement or lack of progression of chest radiographic abnormalities such that no antibacterial therapy is required for the treatment of the current infection.
- **Clinical Failure:** No apparent response to therapy; persistence or worsening of baseline signs and/or symptoms of pneumonia; reappearance of signs and/or symptoms of pneumonia; development of new signs and/or symptoms of pneumonia requiring more than 48 hours of antibiotic therapy other than, or in addition to, study treatment therapy; progression of chest radiographic abnormalities; or death due to pneumonia or death after Day 4 (including) regardless of the reason. If EOT is clinical failure, TOC is also clinical failure.
- **Indeterminate:** Lost to follow-up due to death other than pneumonia at Days 1, 2 or 3, withdrawal, or no assessment.

### 9.2.2.2 cUTI

- **Clinical Cure:** Resolution or substantial improvement of baseline signs and symptoms of cUTI, or return to preinfection baseline if known, such that no antibacterial therapy is required for the treatment of the current infection.
- **Clinical Failure:** No apparent response to therapy; persistence or worsening of baseline signs and/or symptoms of cUTI; or reappearance of signs and/or symptoms of cUTI; development of new signs and/or symptoms of cUTI requiring more than 48 hrs antibiotic therapy other than, or in addition to, study treatment therapy; or death due to cUTI or death after Day 4 (including) regardless of the reason. If EOT is clinical failure, TOC is also clinical failure.
- **Indeterminate:** Lost to follow-up due to death other than cUTI at Days 1, 2 or 3, withdrawal, or no assessment.

### 9.2.2.3 BSI/Sepsis

- **Clinical Cure:** Resolution or substantial improvement of baseline signs and symptoms including a reduction in SOFA score, such that no antibacterial therapy is required for the treatment of BSI/sepsis. Subjects with bacteremia must have eradication of bacteremia caused by the Gram-negative pathogen.
- **Clinical Failure:** No apparent response to therapy; persistence or worsening of baseline signs and/or symptoms, reappearance of signs and/or symptoms; development of new signs and/or symptoms requiring more than 48 hrs antibiotic therapy other than, or in addition to, study treatment therapy; or death due to BSI/sepsis or death after Day 4 (including) regardless of the reason. If EOT is clinical failure, TOC is also clinical failure.
- **Indeterminate:** Lost to follow-up due to death other than BSI/Sepsis at Days 1, 2 or 3, withdrawal or no assessment.

## 9.2.3 Supplementary Clinical Outcomes for Follow-up

### 9.2.3.1 HABP/VABP/HCABP

- **Sustained Clinical Cure:** Continued resolution or substantial improvement of baseline signs and symptoms of pneumonia, such that no antibacterial therapy is required for the treatment of pneumonia in a subject assessed as cured at TOC.
- **Relapse:** Recurrence of signs and/or symptoms of pneumonia, appearance of new signs and/or symptoms of pneumonia, or new chest radiographic evidence of pneumonia or death regardless of the reason in a patient assessed as cured at TOC.
- **Indeterminate:** Lost to follow-up due to death other than pneumonia at Days 1, 2 or 3, withdrawal, no assessment, or received additional antibacterial therapy more than 48 hrs between TOC and FU for the treatment of the current infection.
- **Clinical Failure:** Clinical failure at TOC will be carried forward.

### 9.2.3.2 cUTI

- **Sustained Clinical Cure:** Continued resolution or improvement of baseline signs and symptoms of cUTI, or return to preinfection baseline if known, in a subject assessed as cured at TOC.
- **Relapse:** Recurrence of signs and/or symptoms of cUTI, or appearance of new signs and/or symptoms of cUTI in a subject assessed as cured at TOC.
- **Indeterminate:** Lost to follow-up due to death other than cUTI at Day 1, 2 or 3, withdrawal, no assessment, or received additional antibacterial therapy more than 48 hrs between TOC and FU for the treatment of the current infection.
- **Clinical Failure:** Clinical failure at TOC will be carried forward.

